10.4.3 Treatment Effect Regardless of Non-Study IOP Treatment Use

To evaluate the treatment effect regardless of whether there is any use of non-study IOP lowering treatment, the MMRM analysis for primary analysis in Section 10.1 will be performed in the ITT population using all available Hour 0 IOP data. In this analysis, data after the use of non-study IOP lowering treatment will not be excluded.

10.4.4 Tipping Point Analysis

A tipping-point analysis will be used to assess the robustness of the primary efficacy analysis with respect to possible deviations from missing at random (MAR) assumption in MMRM model. This analysis will evaluate the sensitivity of study results under the missing not at random (MNAR) assumption.

Tipping point analysis will be based on multiple imputed (MI) datasets for IOP data as described in Section 17.2 while applying a shift parameter to imputed IOP data for Bim SR 10 µg treated eyes. Specifically, missing IOP data will be calculated by adding a positive shift value to the imputed data to discount the treatment effect for Bim SR 10 µg. This shift will essentially make the IOP data higher than imputed for Bim SR 10 µg treated eyes. Note that there will be no shift applied to SLT treated eyes. With each shift, the MMRM analysis as specified for the primary efficacy will be performed based on the MI-based but shifted IOP data. SAS PROC MIANALYZE procedure will be used to aggregate the analysis results by using the parameter estimates from each imputed dataset.

Starting from a shift of 0 mmHg (ie, no shift), the above procedures will be repeated with incremental shift values of 1 mmHg. The shift values will be adjusted with unmasked data. The tipping point is reached when the analysis result being switched from positive (ie, Bim SR 10 µg is non-inferior to SLT) to negative (ie, Bim SR 10 µg is no longer non-inferior to SLT). The corresponding shift value is defined as the tipping point. If the IOP value at the tipping point is clinically implausible, the primary analysis results will be considered as robust.

The scientific plausibility, clinical relevance, as well as the interpretations of the different shift values will be discussed in the clinical study report.

10.4.5 Impact of Receiving the 2nd Bim SR After Week 16 and Prior to Week 24

Some patients may receive the second Bim SR 10 µg administration after Week 16 and prior to Week 24, thus the time interval between the second Bim SR 10 µg administration and the primary analysis endpoint at Week 24 will be shorter for these patients as compared with patients who received the second Bim SR 10 µg at Week 16. To evaluate any potential impact of this difference in timing of the second administration on Week 24 IOP data from these patients in the primary analysis, additional sensitivity analysis will be conducted by excluding the IOP data at Week 24 for these patients. More specifically, for patients who received flexible administration of the second Bim SR 10 µg beyond the Week 16 visit, the Week 24 IOP assessment will be excluded from the current sensitivity analysis if the second administration date is in the analysis windows for Week 20 or Week 24 and prior to the Week 24 IOP assessment. The MMRM model for the primary efficacy analysis as described in Section 10.1 will be used.

11.0 SAFETY ANALYSES

All safety analyses will be performed using the safety population. Unless otherwise stated, the last non-missing safety assessment before the SLT treatment (Day 1) will be used as the baseline for all analyses of that safety parameter. As indicated in Section 6.4, safety data collected at Screening for eligibility assessment will not be analyzed.

All safety analyses described in the section 11.0 will be performed both Bim SR 10 µg and Bim SR 15 µg.

Ocular safety will be evaluated through; ocular AEs, best corrected visual acuity, visual field examination, specular microscopy, macroscopic iris color assessment, macroscopic conjunctival hyperemia assessment, gonioscopy/angle assessment, biomicroscopy (using a slit lamp), lens assessment, optic disc examination, dilated ophthalmoscopy, pachymetry, and anterior segment-optical coherence tomography.

Non-ocular safety analysis includes non-ocular adverse events (AEs), clinical laboratory results, vital signs (blood pressure, pulse rate and temperature), and pregnancy test results.

Safety analyses will be summarized by study periods. Analysis study periods are defined as follows:

- **During the study:** Date of SLT treatment through Month 24/Exit visit/last study visit available.
- **Analysis Cycle 1:** SLT Treatment date (Day 1) through the second Bim SR administration date – 1. If the second Bim SR administration was not given to a patient, all safety assessments through Month 24/Exit visit/last study visit available will be included in analysis cycle1.
- **Analysis Cycle 2:** Second Bim SR administration date through Month 24/Exit visit – 1.
- **Analysis Cycle 3:** Third Bim SR administration date through Month 24/Exit visit – 1, valid for only Bim SR 15 µg.

All summaries will be based on the first treatment received in each eye (Bim SR or SLT). If a patient who received both SLT and Bim SR in the same eye, safety assessments will be summarized in Bim SR. For non-ocular safety measures, overall summaries will be presented regardless of study treatment. For ocular safety assessments, summaries will be presented for the periods of during the study, Analysis Cycle 1 and Analysis Cycle 2 as shown in Figure 11-1 below.

Figure 11-1 Analysis Cycle Illustration

| Treatment Schedule | Cycles for Safety Data Analyses | |
|--|---------------------------------|------------------|
| | SLT eye | BIM SR eye |
| Day 1, SLT administration | Analysis Cycle 1 | Analysis Cycle 1 |
| Day 4, Bim SR 1st administration | Analysis Cycle 1 | Analysis Cycle 1 |
| Week 16 ^a , Bim SR 2 nd administration | Analysis Cycle 2 | Analysis Cycle 2 |

| | | |
|--|------------------|------------------|
| Week 32 ^b , Bim SR 3 rd administration | Analysis Cycle 3 | Analysis Cycle 3 |
|--|------------------|------------------|

^a The second administration of Bim SR 10 µg is performed at Week 16 for all patients who meet retreatment criteria. For those patients not meeting retreatment criteria at Week 16, the second administration may be performed during an unscheduled visit after Week 16 and prior to the Month 12 visit if the retreatment criteria are met.

^b Analysis cycle 3 is valid only for Bim SR 15 µg.

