7.0 PATIENT ENROLLMENT, DISPOSITION AND COMPLIANCE

The number of patients in analysis populations (ITT, Safety, and PP) will be summarized for the overall study. The numbers and percentages of patients randomized by country and site will be presented. The numbers and percentages of patients who complete the study and the numbers and percentages of patients who prematurely discontinue the study will be presented overall and by analysis cycle as defined in [Figure 11-1](#), with categories of premature discontinuation reasons included.

The study completers will be defined as the patients who received at least one study treatment and marked as completed in the eCRF disposition page. A patient who received study treatment in the relevant cycle will be considered to have completed the analysis cycle, if (a) the patient is a study completer or (b) the patient received the subsequent study treatment (Bim SR).

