11.1 ADVERSE EVENTS

Adverse events will be coded by system organ class and preferred term using the Medical Dictionary for Regulatory Activities, version 22.0 or newer.

An AE will be considered a treatment-emergent adverse event (TEAE) for the study treatment period if the AE meets one of the following criteria:

- The onset date is on or after the first study treatment date.
- The onset date is before the first study treatment date and either:
 - The severity of the event worsened on or after the first treatment date.
 - The event became serious on or after the first study treatment date.

An AE will be considered as a TEAE for a treatment cycle if the AE meets one of the following criteria:

- The onset date is on or after the treatment administration of the cycle but prior to the next cycle administration.
- The onset date is before the treatment administration of the cycle and either:
 - The severity of the event worsened on or after the treatment administration of the cycle.
 - The event became serious on or after the treatment administration of the cycle.

An ocular AE will be defined by the location information on the adverse event page in eCRF.

An overall summary of patient incidences of TEAEs will be presented by event type and event category (ocular or non-ocular). These summaries will include the following:

- All TEAEs
 - Ocular
 - Non-ocular
- Treatment-related TEAEs:
 - Ocular
 - Related to study drug
 - Related to study drug administration procedure
 - Related to SLT laser
 - Non-ocular
- Treatment-related serious TEAEs:

- Ocular
 - Related to study drug
 - Related to study drug administration procedure
 - Related to SLT laser
- Non-ocular
 - Any TEAEs leading to Bim SR implant removal
 - Any TEAEs leading to study discontinuation
 - Deaths

The following non-ocular TEAEs will be summarized by SOC and PT:

- Any non-ocular TEAEs,
- Any treatment related non-ocular TEAEs,
- Any serious non-ocular TEAEs, and
- Any non-ocular TEAEs leading to study discontinuation.

Ocular TEAEs will be summarized by analysis cycle and by treatment eye as described below:

- Any ocular TEAEs by PT
- Any ocular TEAEs by SOC, PT, and severity
- Any treatment related ocular TEAEs by SOC and PT
- Any serious ocular TEAEs by SOC and PT
- Any ocular TEAEs leading to study discontinuation by SOC and PT
- Any ocular TEAEs within two days of study treatment by SOC and PT

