17.3 ANALYSIS WINDOWS

[Table 17-1](#) provides an overview of efficacy and safety assessments with visit schedule and analysis window table for by-visit and by-cycle analysis.

Table 17-1 Visit Schedule, Visit Windows and By-Cycle Analysis for Efficacy and Safety Assessments

| Efficacy/Safety Assessments | Visit Schedule | Visit Window for by-visit and Analysis Cycle Analysis |
|---|--|--|
| Hour 0 IOP | Baseline, Day 2, W4, W8, W12,W15, W20,W24,W28,W31,W36,W40,W44, W47,W52, M13, M14,M15,M16,M18, M20,M22, M24/EXIT | Table 17-2 |
| Macroscopic conjunctival hyperemia | Baseline, Day2, W4,W8,W12,W15, W20,W24,W28,W31,W36,W40,W44,W47 ,W52,M13,M14,M15,M16,M18,M20,M22 , M24/EXIT | Table 17-2 |
| BCVA | Baseline, Day 2, W4, W8, W12, W15, w20,W24,W28,W31,W36,W40,W44, W47,W52,M13,M14,M15,M16,M18,M20, M22,M24/EXIT | Table 17-2 |
| Visual field | Baseline, W24,W52,M18,M24/exit | Table 17-4 |
| Specular microscopy | Baseline, W4, W12, W24, W40, W52,M16,M20, M24/Exit | Table 17-3 |
| Biomicroscopy | Baseline, Day2, W4, W8,W12,W15, W20,W24,W28,W31,W36,W40,W44, W47,W52, M13,M14,M15,M16,M18, M20,M22, M24/EXIT | Overall by-cycle summary |
| Gonioscopy/ Angle assessment | Baseline,W4(optional),W8,W12(optional), W15,W20,W24(optional),W28,W31,W36, W40,W44,W47,W52,M13,M14,M15,M16, M18,M20,M22,M24/EXIT | Table 17-2 |
| Pachymetry | Baseline, W4, W12, W24, W40, W52, M16, M20, M24/EXIT | Table 17-3 |
| Optic disc/ Ophthalmoscopy/ Lens assessment | Baseline, W12, W24, W40, W52, M16, M20, M24/EXIT | Table 17-3 |

[Table 17-2](#) presents the visits assigned for by- visit and analysis cycle analyses of the efficacy (Hour 0 IOP), and safety assessments that occur every month (or 2 months after 1-year of follow-up after the first Bim SR administration), including of macroscopic conjunctival hyperemia, best-corrected visual acuity, biomicroscopy, and gonioscopy/angle assessment. [Table 17-3](#) presents the visit assigned for by-visit and analysis cycle that occur every 3 or 4 months, including of specular microscopy, pachymetry and optic disc assessments which occur every 3 or 4 months. [Table 17-4](#) presents the visits assigned for by-visit and analysis cycle analyses of visual filed, ophthalmoscopy, optic disc, and lens assessments which occur every 6 months.

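### SAP 11.0 ends Analysis Cycles 2 and 3 one day before the exit visit, so a retreated patient's exit visit belongs to no analysis cycle

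*SAP*

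**What the plan says.** SAP 11.0 defines a whole-study period and up to three analysis cycles for safety.

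- Cycle 1, retreated patient: "SLT Treatment date (Day 1) through the second Bim SR administration date – 1". Cycle 2 then opens on the day of the second implant.
- Cycle 1, never-retreated patient: "all safety assessments through Month 24/Exit visit/last study visit available will be included in analysis cycle1".
- Cycle 2: "Second Bim SR administration date through Month 24/Exit visit – 1". Cycle 3 starts at the third administration and has the same end. Neither definition mentions the last available visit.
- The section covers both dose strengths ("All safety analyses described in the section 11.0 will be performed both Bim SR 10" µg and 15 µg). Note b to Figure 11-1 limits the third cycle to the higher one: "Analysis cycle 3 is valid only for Bim SR 15" µg.

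Other SAP text bears on where a cycle ends.

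- The whole-study period in 11.0 runs through the exit or last visit.
- In Table 17-2 the last Cycle 2 row takes every day after 585, and the last Cycle 3 row every day after 465. Notes d and e to Table 17-3 apply these windows to the assessments made every 3 to 4 months.
- Section 17.5 uses every postbaseline assessment for safety evaluation.
- Section 11.1 assigns an adverse event to a cycle by this rule: "The onset date is on or after the treatment administration of the cycle but prior to the next cycle administration". It sets no cut-off at exit.

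**The concern.** In Cycle 1 the subtraction of one day is right, because the next cycle begins on the following day. In Cycles 2 and 3 nothing begins at exit, so the same subtraction leaves the exit visit outside every cycle. Only patients who were retreated are affected.

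The stake is the set of descriptive within-cycle summaries that are not adverse-event tables:

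- greatest endothelial cell density decrease (11.3.5);
- largest visual acuity line loss (11.3.2);
- implant contact with the corneal endothelium (11.3.10);
- biomicroscopy, which Table 17-1 assigns no window table, only "Overall by-cycle summary".

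These report worst values or occurrence at any visit. Removing a visit can leave a patient's result unchanged or make it look better, but never worse. The visit removed is the one furthest from the second implant. Implant contact depends most on the cycle definition, because 11.3.10 asks for that count by cycle only (a general sentence in 11.0 also provides for whole-study ocular summaries). One programmer working from 11.0 and another from Table 17-2 would produce different Cycle 2 tables.

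A second defect sits in the same lines. Cycle 2 does not stop at a third administration, so a patient with three implants has the same data in Cycles 2 and 3.

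**Working it through.** No sample size or power figure is involved. The check applies the 11.0 boundaries literally and compares the result with the window tables.

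**Inputs**

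- Table 17-2 target days, counted from the first implant: Week 12 = 81, Week 20 = 137, Week 24 = 165, Week 40 = 277, Week 52 = 361, Month 16 = 477, Month 20 = 597, Month 22 = 657, Month 24 = 717.
- The weekly targets follow 7 × week − 3, so Week 16 = 7 × 16 − 3 = 109 and Week 32 = 7 × 32 − 3 = 221.
- Protocol visit windows: Week 16 −2/+4 days (Table 4); Months 22 and 24 ±7 days (Table 6).
- Day within a cycle = visit day − implant day + 1.

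**Cycle holding the exit visit**

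| Patient | 11.0 read literally | Table 17-2 |
|---|---|---|
| Never retreated | Cycle 1 | Cycle 1 |
| Two implants (second at Week 16) | none | Cycle 2, last row |
| Three implants (third at Week 32) | Cycle 2 ends the day before exit, Cycle 3 likewise: none | Cycle 3, last row |

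**Second implant at Week 16 (day 109)**

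- Exit: 717 − 109 + 1 = 609. Month 22: 657 − 109 + 1 = 549. Month 20: 597 − 109 + 1 = 489.
- With visit windows the second implant falls on days 107 to 113 and exit on days 710 to 724. The earliest exit is 710 − 113 + 1 = 598 and the latest is 724 − 107 + 1 = 618.
- The latest Month 22 visit is 664 − 107 + 1 = 558.
- Exit is therefore the only scheduled visit that can exceed day 585. Under literal 11.0 no scheduled visit can fill the last Cycle 2 row; an unscheduled visit still could.
- With exit on target this holds for a second implant up to day 132 (717 − 132 + 1 = 586). After a later implant, exit falls in an earlier Cycle 2 row but is still cut.

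**Scheduled cell counts left after the second implant** (days 165, 277, 361, 477, 597, 717)

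| Day of second implant | Counts in Cycle 2 | Lost under 11.0 |
|---|---|---|
| 109 to 164 | 6 | 1 of 6 |
| 166 to 276 | 5 | 1 of 5 |
| 278 to 360 | 4 | 1 of 4 |

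After Week 16 retreatment the last count kept is on day 489 instead of day 609, a gap of 609 − 489 = 120 days.

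**Gonioscopy after Week 16:** 9 visits from Week 20 to Week 52, plus 8 from Month 13 to Month 24, gives 17. The loss is 1 of 17, or 1 of 14 if Months 13, 15 and 22 are skipped as protocol 8.4.3.11 allows.

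**Early leavers:** protocol 8.9 has the exit procedures done at the last visit. A patient retreated at Week 16 who leaves at or before Week 24 has the exit count as the only such count in Cycle 2.

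**Third implant at Week 32 (day 221)**

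- It falls on Cycle 2 day 221 − 109 + 1 = 113. Literal Cycle 2 ends on day 608, so 608 − 113 + 1 = 496 days lie in both cycles.
- Exit is Cycle 3 day 717 − 221 + 1 = 497, in the row above 465. Month 22 is day 437, at most 444, in the row before it.

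**The case against.** The strongest reply is that the SAP already handles this. Section 17.3 presents Table 17-1 as the guide for by-visit and by-cycle analysis, and it sends acuity, hyperemia, gonioscopy, specular microscopy, pachymetry and optic disc to tables whose last windows stay open. A programmer who follows those tables keeps the exit visit. That is true, but no rule ranks the tables above 11.0, and biomicroscopy has no window table. The reply confirms that two instructions conflict.

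On the overlap, 11.0 lists only the whole study and Cycles 1 and 2 for ocular summaries, so nothing may be counted twice in what is presented. Even so, Cycle 2 as written would contain data collected after a third implant. Section 11.1 closes a cycle at the next administration. Figure 11-1 shows which administration opens each cycle, and 7.0 counts a cycle as complete if "the patient received the subsequent study treatment (Bim SR"); these give weaker support, because neither sets an end date for safety data.

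Two further points stand. The shares above count visits and do not measure a change in any result: a summary moves only if exit holds the worst value or the only contact. Contact first seen at a completer's exit is also unlikely after Week 16 retreatment, because protocol 1.2 expects the polymer to degrade within about 12 months and day 609 is about 20 months after that implant. Early exits and late retreatments remain possible.

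**Conclusion.** The concern holds: 11.0 is wrong as written and contradicts other parts of the SAP. It is minor. Read literally, every retreated patient who has exited by a given lock loses that visit, in both eyes, from the within-cycle tables. That means early leavers, any 15 µg patients already finished, and at the final lock all retreated patients with an exit visit. The documents give none of these numbers, nor how often exit holds the worst value, so the effect on any table is unknown.

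The overlap concerns only those of the 55 patients on 15 µg who received three implants; that number is not given either.

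Not affected are efficacy, by-cycle adverse events, whole-study summaries, the last-visit cell density table, the Kaplan-Meier and exposure-adjusted cell-loss analyses, and the listing of losses of 20% or more. The exit data still appear there.

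The day counts assume visits on target unless a window is stated, and take Weeks 16 and 32 from the spacing of Table 17-2. The finding itself needs no assumption beyond the literal text. That the subtraction was carried over from the Cycle 1 wording is only a guess.

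**What to change.** Replace two definitions in SAP 11.0:

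- Analysis Cycle 2 runs from the date of the second Bim SR administration to the day before the third if one was given; otherwise it runs to the exit visit or last available visit, with that visit included.
- Analysis Cycle 3 runs from the date of the third administration to the exit visit or last available visit, with that visit included.

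This brings 11.0 into line with 11.1, the last windows of Table 17-2 and notes d and e of Table 17-3. The cost is two lines of text and one derivation. No other analysis changes.

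### For 15 µg patients given a third implant, the SAP's Analysis Cycle 2 does not stop at that implant, so visit-based by-cycle ocular summaries count later findings under Cycle 2

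*SAP*

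**What the plan says.** SAP 11.0 applies its safety analyses to both dose strengths and then defines the periods. Cycle 1 is "SLT Treatment date (Day 1) through the second Bim SR administration date", less one day. Cycle 2 is "Second Bim SR administration date through Month 24/Exit visit", less one day. Cycle 3 is "Third Bim SR administration date through Month 24/Exit visit", again less one day, and is for 15 µg only. Later in the same section, for ocular assessments, "summaries will be presented for the periods of during the study, Analysis Cycle 1 and Analysis Cycle 2 as shown in Figure 11-1". Figure 11-1 assigns the Week 32 third administration to Cycle 3 for both eyes, with a footnote that begins "Analysis cycle 3 is valid only for Bim SR 15" µg. Tables 17-2 and 17-3 give visit windows for Cycle 3.

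Two other rules tie the end of a cycle to the next implant. SAP 11.1 assigns a new-onset adverse event to a cycle if it starts "on or after the treatment administration of the cycle but prior to the next cycle administration". SAP 7.0 treats a patient as having completed an analysis cycle once the subsequent Bim SR treatment is given.

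Third implants did occur or could have occurred. The Protocol Summary limits Stage 1 to two cycles only for patients who had not had a third before Amendment 3 was implemented. SAP 15.0 gives 55 patients treated at 15 µg. Neither document says how many of them had three implants.

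**The concern.** Several by-cycle ocular summaries take the worst value or any occurrence within the cycle: the largest visual acuity line loss (SAP 11.3.2), the greatest endothelial cell density decrease (11.3.5) and implant contact with the corneal endothelium at any visit (11.3.10). One finding after the third implant can set the Cycle 2 result for an eye. The Cycle 2 column at 15 µg would then mix experience after two implants with experience after three, under a label that refers to the second.

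This matters for how ocular safety is read against the number of implants at the higher dose. The time-to-event and exposure-adjusted endothelial analyses in SAP 11.3.5 are worded for 10 µg and SLT eyes, although 11.0 opens by applying all safety analyses to both strengths. If they are run for 10 µg only, the by-visit and by-cycle tables carry most of the 15 µg endothelial evidence.

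The SLT eye uses the same cycle dates (Figure 11-1), so the comparison between eyes still covers the same calendar time. What is blurred is attribution to the second or the third implant.

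**Working it through.** The plan states no figure for this point, so the check compares the definitions and then sizes the overlap.

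**1. Definitions side by side.**
- Cycle 1 ends at the next implant minus 1 day.
- Cycle 2 ends at Month 24/Exit minus 1 day, whether or not there is a third implant.
- Cycle 3 has the same end as Cycle 2 and starts later, so it lies wholly inside Cycle 2.
- New-onset adverse events (11.1): the cycle ends at the next administration.
- Adverse events more than two days after treatment (11.1): the table ends at the next Bim SR or sham treatment.
- Disposition (7.0): the cycle is complete when the next Bim SR is given.

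The Cycle 2 line is the exception. As written, a patient could have completed Cycle 2 in the disposition table while later examinations were still summarised as Cycle 2.

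**2. Days, counted from the first Bim SR administration.** Table 17-2 target days for the scheduled weeks follow 7 × week − 3 (Week 4 = 25, Week 24 = 165, Week 52 = 361). Assume implants exactly at Weeks 16 and 32 and follow-up to the Month 24 target.
- Second implant: 7 × 16 − 3 = 109.
- Third implant: 7 × 32 − 3 = 221.
- Month 24 target: 717, so the last day of Cycles 2 and 3 is 716.
- Cycle 2 as written: 716 − 109 + 1 = 608 days.
- Part after the third implant: 716 − 221 + 1 = 496 days, and 496/608 = 82%.
- Cycle 2 if it stopped at the third implant: 220 − 109 + 1 = 112 days.

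**3. Visits.** In the current schedule there are 16 regular visits from Week 20 to Month 22, of which 12 come after Week 32. The Protocol's list of tables names a separate schedule for patients who reached Week 32 before Amendment 3 was implemented. That table is not in the text available here, so the counts for these patients may differ.

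**4. Windows.** Counted from the second implant, the third falls on day 221 − 109 + 1 = 113. Table 17-2 has 21 Cycle 2 rows from Week 4 on, and 17 of them have a target after day 113. As an example, take the Week 40 visit at day 277:
- from the second implant, 277 − 109 + 1 = 169, which is Cycle 2 Week 24 (window 155 to 182);
- from the third implant, 277 − 221 + 1 = 57, which is Cycle 3 Week 8 (window 43 to 70).

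The same examination fits both rows. SAP 17.3 has rules for several visits in one window, but none for one visit that fits two cycles.

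**The case against.** A reader might infer that all harm after the third implant is reported as harm of the second. The documents do not support that. A new-onset event after the third implant is kept out of Cycle 2 by SAP 11.1. If Cycle 3 tables were not produced, such events would appear only in the whole-study summary: attribution would be lost, but not moved to the second implant. There is one small exception. The worsening criterion, "The severity of the event worsened on or after the treatment administration of the cycle", has no upper limit, so an event that began before the second implant and worsened after the third can still count in Cycle 2.

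A reader might also infer that the plan drops Cycle 3. It does not. Cycle 3 is in the period list of 11.0, in Figure 11-1 (which the ocular sentence itself cites) and in Tables 17-2 and 17-3. The sentence contradicts the rest of the SAP.

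Nor is it right that the information could not be recovered. Endothelial density and pachymetry are also summarised by visit, with Cycle 3 windows. Patients with at least 20% endothelial cell loss are listed (11.3.5), and all safety assessments go into listings (17.5).

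Other parts of the objection stand. The rules in 7.0 and 11.1 suggest that cycles were meant to end at the next implant, so this looks like an omitted clause and not a deliberate choice. The 82% is a share of nominal calendar days, not a measure of bias. No hypothesis test depends on these tables. Stopping Cycle 2 at the third implant also creates unequal follow-up: about 112 days for three-implant eyes against about 608 for two-implant eyes.

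None of this removes the defect. A programmer who follows the Cycle 2 definition literally will put post-third-implant examination findings in Cycle 2.

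**Conclusion.** The Cycle 2 definition in SAP 11.0 is wrong as written for 15 µg patients who received a third implant. It overlaps Cycle 3 completely and conflicts with the Cycle 1 definition, SAP 7.0 and the new-onset rule in 11.1. The omission of Cycle 3 from the ocular summary periods is a separate internal contradiction.

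The effect is confined to visit-based by-cycle ocular summaries in the separately reported 15 µg safety results. It concerns at most 55 patients, and probably fewer, since Amendment 3 ended third administrations for anyone who had not yet had one. The 496 of 608 days assume implants exactly at Weeks 16 and 32 and follow-up to the Month 24 target day. They show how much of Cycle 2 is open to the misassignment, not how far any result would change.

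**What to change.** - In SAP 11.0, end Analysis Cycle 2 at the third Bim SR administration date minus 1 when a third is given, and otherwise at Month 24/Exit minus 1 as now.
- In the sentence that lists the ocular summary periods, add Analysis Cycle 3 for 15 µg only.
- In Tables 17-2 and 17-3, add a note that Cycle 2 windows stop the day before a third administration.
- Footnote the 15 µg by-cycle tables to say that Cycle 2 follow-up is shorter for three-implant eyes than for two-implant eyes.

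A 15 µg corneal table by number of implants received is optional. If made, it should include a one-implant category, since SAP 11.0 provides for patients who never had a second administration.

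The cost is a few lines of SAP text and one more column in the 15 µg tables, with no new data and no change to the 10 µg analyses. The downsides are small cells in Cycle 3 and the unequal Cycle 2 follow-up that the footnote discloses.
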